9.4. Safety Assessments

Safety monitoring will be performed throughout the study for all subjects. All AEs, regardless of causality or severity, will be recorded on the AE CRF. CAM2038 injections may be discontinued as clinically indicated.

9.4.1. Adverse Events and Serious Adverse Events

The following definitions, developed in accordance with the United States (US) Code of Federal Regulations (CFR) and the International Conference on Harmonization (ICH) Clinical Safety Data Management Guidance for Industry, E2A, will be used for the purpose of identifying AEs in this clinical study.

An AE is any untoward medical occurrence in a subject administered a pharmaceutical product that does not necessarily have a causal relationship with this treatment. An AE can therefore be any unfavorable and unintended sign (e.g., including an abnormal laboratory finding), symptom, or increase in severity of a preexisting abnormality, temporally associated with the use of a medicinal (investigational) product, whether or not considered related to the medicinal (investigational) product.

9.4.1.1. Adverse Event Reporting

All AEs (except for withdrawal symptoms, see below) must be entered on the AE CRF, regardless of causality or severity. AEs include new AEs, worsening baseline conditions, clinically significant laboratory findings, disease-related signs and symptoms that were not present at baseline, and any events or findings that the Investigator feels are clinically significant. Withdrawal symptoms will be captured via specified assessments and should not be recorded as AEs.

Disease-related signs and symptoms that are present at baseline should not be recorded as AEs unless they worsen in severity or increase in frequency.

Information collected concerning AEs will include the following:

- Name of the event
- Onset date
- Resolution date
- Severity (i.e., mild, moderate, or severe)
- Relationship to study drug
- Action and outcome
- Seriousness of event

Definition of MILD, MODERATE, SEVERE AE:

- Mild- An AE that requires minimal treatment and does not interfere with daily living.
- Moderate- An AE that requires therapeutic intervention and interferes with daily living.
- Severe- An AE that requires intensive therapeutic intervention, significant, etc.

All AEs will be documented and followed from the time the subject has signed the ICF until 14 days after the Follow-up Visit (or 30 days after early termination). Serious AEs and AEs that have been designated as possibly related to study drug will be followed until resolution or stabilization.

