9.4.1.2. Serious Adverse Event (SAE)

An SAE or reaction is any adverse drug experience occurring at any dose that results in any of the following outcomes:

- Death
- Is life-threatening (at the time of the event)
- Requires inpatient hospitalization or prolongation of existing hospitalization,
- Results in persistent or significant disability/incapacity
- Is a congenital anomaly/birth defect (in an offspring)

- An Important medical event that may not result in death, be life-threatening, or require hospitalization may be considered an SAE when, based upon appropriate medical judgment, the event may jeopardize the subject and/or may require medical or surgical intervention to prevent one of the outcomes listed in this definition.

All AEs requiring hospitalization or prolongation of a pre-existing hospitalization should be reported as SAEs unless they occur greater than 14 days after the Follow-up Visit (or 30 days after early termination) AND are not considered to be drug-related by the Investigator.

Hospitalizations meeting the following criteria will not be reported as an SAE but must be recorded on the appropriate CRF: study specified hospitalization, short-term administrative hospitalization for procedures, tests or treatments of conditions that would not otherwise constitute an SAE, elective hospitalizations.

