9.4.1.2.1. Serious Adverse Event Reporting

Serious AEs must be reported to the Sponsor or designee within 24 hours of knowledge of the event. All SAEs that occur while a subject is receiving study drug and within 14 days following the Follow-up Visit (or 30 days after early termination) are reportable within 24 hours. During the follow-up period beyond 14 days from Follow-up (or 30 days after early termination), only those SAEs that are considered to be possibly related to study drug should be reported within 24 hours.

The procedure for reporting an SAE is as follows:

- Within 24 hours of knowledge of the event, the site must contact the Sponsor (or designee) by telephone or facsimile to report the event.
- The initial report should include all information known at the time of the report (additional information can be reported as discovered). Do not delay the initial reporting in order to obtain resolution or follow-up information.
- The site will enter into the electronic database (or fax, if the database cannot be accessed for any reason) an SAE report, or similar form, that includes the following information, as available:
 - Subject ID
 - Basic demographic information (age, gender, weight)
 - Outcomes attributed to the event (death, life-threatening hospitalization [new or prolonged], disability, congenital anomaly, required medical intervention to prevent permanent impairment/damage, etc.)
 - Onset date and severity of the event
 - Brief description of the event including frequency and severity of symptoms leading to diagnosis
 - List of relevant test results and laboratory data
 - Any other relevant history
 - Whether the study drug was discontinued

- Whether the assigned treatment oral or injectable therapy was discontinued and/or dose titration discontinued, as applicable
- Investigator's assessment of causality

The Medical Monitor or another representative of the Sponsor may contact the Investigator to request additional information regarding the event or to confirm information. All SAEs will be entered on the AE CRF. The same nomenclature should be used on both the SAE report and the AE CRF.

Specific instructions for SAE reporting and a copy of an SAE report form are provided in the MOP.

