The Investigator is responsible for the complete and timely reporting of all SAEs to the Sponsor (or designee), reporting pertinent follow-up information on the SAE, and notifying the appropriate IRB/Independent Ethics Committee (IEC) of the occurrence of and details surrounding the event. In the event there is a question as to whether the AE is serious, the event should be reported.

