11.1.2 ADVERSE EVENTS

Each AE and serious adverse event (SAE) term recorded on the CRFs by primary system organ class (SOC) and will be mapped to a preferred term (PT) using the MedDRA dictionary. The Investigator will assess AE severity and relationship to the study treatment.

A treatment-emergent adverse event (TEAE) is defined as any AE with an onset date on or after the date of the first study treatment, or any ongoing event started on the date of the first dose that worsens in severity. Only AEs with an onset date prior to the date of the last dose + 30 days will be tabulated in summary tables. For the purpose of calculating treatment emergence and inclusion in summary tables, incomplete onset dates will be imputed as detailed in Appendix B.

AEs will be summarized by the number and percent of patients in each primary SOC and PT. Patients will be counted only once for each primary SOC and each PT. Summary tables of AEs by primary SOC, PT and intensity will be provided. If a patient has more than one AE coded to the same PT, the patient will be counted only once for that PT by using the event with the highest intensity. Similarly, if a patient has more than one AE within a primary SOC category, the patient will be counted only once in that SOC category by using the event with the highest intensity. AEs by primary SOC, PT and relationship to study drug will be provided as well. If a patient has more than one AE coded to the same PT, the patient will be counted only once for that PT by using the most related event. Similarly, if a patient has more than one AE within a primary SOC category, the patient will be counted only once in that primary SOC category by using the most related event. In addition, SAEs by primary SOC and PT will be provided. Deaths and SAEs will be summarized similarly to AEs. All AE tables will also include the total number of events, counting multiple events per patient.

Injection-related AEs, other (non-injection related) AEs as well as all AEs will be presented. Summaries of these AE subsets will be presented for the following categories:

- Study drug-related
- Intensity
- Serious
- AEs which led to treatment/study discontinuation
- SAEs which led to treatment/study discontinuation
- AEs occurring in 5% or greater of patients (by preferred term)

In the AE summary, the SOCs and the PTs within each SOC will appear in descending order of frequency.

Frequencies of deaths and hospitalizations will also be summarized.

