11.1.7 INJECTION SITE EXAMINATION

The injection site will be visually inspected for evidence of erythema, edema, itching, pain, infection, bleeding, abnormal healing and any other abnormalities.

AEs that are believed to be associated with injection procedures will be summarized similarly to the summaries for other AEs (not associated with injection procedures).

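### Non-serious withdrawal that ends treatment is kept out of the AE tables, and the protocol gives two conflicting COWS/SOWS schedules for weekly dosing

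*Protocol*

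**What the plan says.** **AE recording.** Protocol 9.4 sets the general rule: "All AEs, regardless of causality or severity, will be recorded on the AE CRF". Section 9.4.1.1 repeats it with withdrawal symptoms carved out, and then says: "Withdrawal symptoms will be captured via specified assessments and should not be recorded as AEs". The same section also counts as AEs "any events or findings that the Investigator feels are clinically significant". For baseline disease signs it gives a limit: they become AEs if they worsen or become more frequent. Withdrawal symptoms get no such clause.

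**Serious events.** Protocol 9.4.1.2 opens with "An SAE or reaction is any adverse drug experience occurring at any dose that results in any of the following outcomes". Section 9.4.1.2.1 adds "All SAEs will be entered on the AE CRF" and "In the event there is a question as to whether the AE is serious, the event should be reported".

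**Tabulation.** SAP 11.1.2 takes as its source "Each AE and serious adverse event (SAE) term recorded on the CRFs". From these it plans summaries that include drug-related AEs and AEs leading to discontinuation of treatment or study. SAP 8.1 tabulates reasons for early discontinuation. COWS and SOWS are listed under efficacy (Protocol 9.7, SAP 10.1.1) and not among the safety variables (Protocol 9.6).

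**Schedule.** Protocol 7.1.2.3 lists COWS, SOWS and the Desire and Need to Use VAS among the items assessed at every weekly or monthly visit. Table 3 has one row for these scales and marks it monthly in both ongoing q1w columns. Section 7.1.2.3 also makes the scores part of the decision to move a patient from q1w to q4w, which may be taken at any weekly visit.

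**The concern.** Tolerability is part of the primary objective (Protocol 6.1). In this single-arm study it is read mainly from the AE tables, above all those for drug-related AEs and AEs leading to discontinuation. Withdrawal bad enough to make a patient stop a buprenorphine depot is a tolerability outcome, yet the recording rule keeps the non-serious form of it out of those tables.

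The rule relies on specified assessments instead, evidently COWS and SOWS (Protocol 9.3.5). These carry no causality assessment and are summarised only in the Efficacy Population. That population requires some post-baseline efficacy measurement (SAP 5.3), so a patient who stops very early without one is missing there too. For weekly-dosed patients the protocol also contradicts itself on how often the scales are completed. Under Table 3, AEs are collected weekly in these patients, while the measure that replaces AE recording of withdrawal is collected monthly.

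**Working it through.** **1. Following a withdrawal case through the rules.** The plan states no figure on this point, so there is none to reproduce.

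- *Serious.* It meets an outcome in 9.4.1.2, is reported, and goes on the AE CRF under 9.4.1.2.1. It reaches the tables.
- *Non-serious, treatment continues.* It is scored on COWS/SOWS only. This is the intended effect of the exclusion.
- *Non-serious, and the reason for stopping.* It is barred from the AE CRF by 9.4.1.1. There is then no AE term for SAP 11.1.2 to use and no relatedness field to complete. It can appear as a disposition reason (Protocol 11.3.1, SAP 8.1) and in Listing 16.2.3.

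Only the third case is a gap.

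**2. Tables affected (SAP Appendix A).** The drug-related set is 14.3.3.1 to 14.3.3.6 and the discontinuation set is 14.3.7.1 to 14.3.7.6, which is 12 tables.

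- Remove the 6 Full Exposure tables (those ending .2, .4 and .6 in each set). That population has by definition been exposed for 48 weeks (SAP 5.2), so its members did not stop early.
- Remove the 2 remaining injection-related tables (14.3.3.3 and 14.3.7.3). SAP 11.1.7 ties that category to the procedure: "AEs that are believed to be associated with injection procedures will be summarized similarly to the summaries for other AEs".
- 12 − 6 − 2 = 4: tables 14.3.3.1, 14.3.3.5, 14.3.7.1 and 14.3.7.5.

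The two drug-related tables are affected only where the event would have been judged related. The four tables largely repeat the same events, so the count is of outputs and not of cases.

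**3. COWS/SOWS schedule for a patient who stays on q1w.**

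- Weekly visits after Day 1, Weeks 2 to 48: 48 − 1 = 47.
- Under the text of 7.1.2.3, all 47 have a score.
- Under Table 3, with monthly taken as every four weeks:
  - scores at Weeks 5, 9, ..., 45: (45 − 5)/4 + 1 = 11, leaving 47 − 11 = 36 unscored, and 36/47 = 76.6%;
  - scores at Weeks 4, 8, ..., 48: (48 − 4)/4 + 1 = 12, leaving 47 − 12 = 35 unscored, and 35/47 = 74.5%.

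The monthly entry does not look like an extraction fault. The neighbouring urine toxicology and self-report rows read weekly in the same two columns.

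**The case against.** The exclusion is a deliberate design choice. It is stated twice, it names a replacement method, and Protocol 9.5 says the scales are there to check that withdrawal is controlled. That stands. Sections 9.4 and 9.4.1.1 are best read as rule and exception. The clause on clinically significant findings is not a firm contradiction either: the explicit bar follows it and is the more specific text. If a site gave that clause priority, the gap would shrink, but sites could then differ.

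Cases that end treatment are also not lost. Discontinuation reasons are tabulated and listed, and booster injections are recorded with reasons (Protocol 9.3.7). This stands too, but none of these records gives relatedness or feeds an AE table. The Manual of Procedures is not available here and might contain a fuller rule.

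A reader might infer that serious withdrawal also goes unreported. The documents do not support this, since the SAE rules give it a route. What they leave open is whether a diagnosed withdrawal reaction counts as an excluded symptom.

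On the schedule, Protocol section 9 says assessments follow Table 3, and 7.1.2.3 also refers q1w visits to it, so Table 3 may be meant to govern. That does not remove the each-visit list in 7.1.2.3. A reader might further infer that patients could be switched to q4w without a score. That does not follow, because 7.1.2.3 has the criteria considered on the day of the switch, which implies scoring then. Table 3 simply does not show it.

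**Conclusion.** The point holds in a narrow form. Followed as written, the protocol keeps non-serious withdrawal that ends treatment out of four Overall Safety AE tables, and a disposition reason is the main remaining trace. Separately, the two COWS/SOWS/VAS schedules for weekly dosing differ at 35 or 36 of 47 visits (74% to 77%), assuming a four-week month and a patient who stays on q1w throughout.

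Two stronger readings should be avoided. A reader might add the Full Exposure drug-related tables to the count, but a patient in that population cannot have stopped early because of withdrawal. A reader might also take a rate from the earlier study in Protocol 5.1.2, where a withdrawal reaction was handled as a related SAE. That event occurred at 192 mg under naltrexone and was also attributed to naltrexone, so it gives no rate for this trial. It shows only that the programme has treated withdrawal as an event with assessed causality. The documents do not say what share of the expected dropout is due to withdrawal, so the number of patients affected cannot be projected.

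This should be corrected, but it does not undermine the study.

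**What to change.** **1. Limit the exclusion in Protocol 9.4.1.1.** Keep it for withdrawal symptoms scored on the scales. Add that a withdrawal event that is serious, or is the recorded reason for discontinuing treatment, is entered as an AE (as an SAE where the criteria are met) with relatedness assessed. Both triggers are recorded facts, which leaves less room for sites to differ than a test of clinical significance would.

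*Cost:* a short protocol clarification and CRF completion guidance, with no new table. There would be a few more AE entries, and some events would appear both as AEs and as scores. If the change is made mid-study, earlier discontinuations would need review against their disposition reason so that data before and after are comparable.

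**2. Reconcile Protocol 7.1.2.3 with Table 3** for COWS, SOWS and the Desire and Need to Use VAS in weekly-dosed patients. Table 3 should show scoring at any visit where 7.1.2.3 relies on the scores for a switch. No view is taken on the routine frequency.

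*Cost:* a text and table edit. Any change in the number of assessments depends on which frequency was intended.

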7.6. Removal of Subjects from Therapy or Assessment

A subject is free to withdraw his/her consent and discontinue participation in the study at any time for any reason. A subject's participation must therefore be terminated immediately upon his/her request, and the reason(s) for discontinuation appropriately documented.

A subject must be discontinued from the study for any of the following reasons:

- Safety reasons, including AEs or significant concomitant illness, increased concomitant use of recreational drugs, alcohol, psychotropic agents or methadone, injury, or urgent surgeries/procedures that would, in the judgment of the Investigator, affect assessments of clinical status to a significant extent, require discontinuation of study drug, or both
- At the request of the Sponsor, regulatory agency, or Institutional Review Board (IRB)
- Subject is lost to follow-up
- Pregnancy (UK only)
- Death of subject

A subject may also be discontinued from the study, at the discretion of the Investigator and/or Sponsor, for any of the following reasons:

- Subject refuses or is unable to adhere to the study protocol
- Protocol violation
- Pregnancy (in the UK, pregnant subjects must be discontinued, see above)
- Requirement for continual use of opioid analgesics >7 days or requirement for general anesthesia for surgery

The Investigator must maintain a record of all subjects who discontinue from the study prior to completion; the reason(s) for study discontinuation will be documented. In the event that a subject chooses to withdraw from the study, the Investigator should make a reasonable attempt to obtain and record the reason(s) for withdrawal, if possible, although the subject is not obligated to provide such a reason.

All efforts should be made by the Investigator to continue collection of safety assessments at the protocol-defined study visit intervals, including concomitant medications, and AEs in subjects that discontinue study drugs, unless the subject withdraws his/her consent at the time of early discontinuation. The Investigator should also ask the subject to return for the Follow-up assessments, provided that the subject has not withdrawn consent for those assessments. If a subject refuses to complete early termination procedures and/or Follow-up, this information will be recorded.

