^m A complete physical exam of all major body systems will be performed at the Screening Visit.

Study Phase:	Screening	Treatment Phase						EOT	Follow-up	
Treatment:	-	CAM2038 q1w or q4w	CAM2038 q1w			CAM2038 q4w				All Subjects
Study Population:	All Subjects ^a	All Subjects	New to BPN Treatment ^b	Transition from SL BPN/BPX ^c	Transition from CAM2038 q1w ^d	Transition from SL BPN/BPX (Monthly) ^e				
Month ^f :	M-1	M1	M1	M1 to Mx	M1 to Mx	Mx to M12 ^g	M1 to M12 ^h		M13	
Week ^h :	-3	W1	W1	W2 to Wx ⁱ	W1 to Wx ⁱ	Wx to W48	W1 to W48		W49	
Day:	-	Day 1	Day 2-7 ^j	-	-	-	-		-	
Weight, BMI	X	X		Monthly	Monthly	Monthly	Monthly			
Height	X									
Abbreviated Review of Systems		X							X	
Vital Signs ⁿ	X	X		Weekly	Weekly	Monthly	Monthly		X	
ECG	X			X ^o	X ^o	X ^o	X ^o		X	
Laboratory tests ^p	X								X	
Pregnancy Test ^q	X	X		Weekly	Weekly	Monthly	Monthly		X	
Hepatitis B/C, HIV ^r	X									
Injection Site Examination		X		Weekly	Weekly	Monthly	Monthly		X	
Dispense Treatment ID Card		X								
Urine Toxicology	X	X		Weekly	Weekly	Monthly	Monthly		X	
Illicit Drug Use Self-Report	X	X		Weekly	Weekly	Monthly	Monthly		X	
SOWS, COWS VAS	X	X	(X)	Monthly	Monthly	Monthly	Monthly		X	
EQ-5D-5L	X	X		Monthly	Monthly	Monthly	Monthly		X	

ⁿ Includes temperature, blood pressure, pulse rate, respiration rate.

^o ECG will be performed after the first administration of CAM2038 q1w or CAM2038 q4w (i.e., prior to dosing at Week 2 for CAM2038 q1w or Week 5 for CAM2038 q4w). During the study, ECGs will be performed after dose increases (excluding the initial dose titration and booster injections) and after intake of QT-extending drugs or CYP3A4 inhibitors.

^p Includes chemistry, hematology, urinalysis and coagulation profile.

^q A serum pregnancy test will be performed at Screening and EOT (Week 49). An “in-office” urine pregnancy test will be required at Day 1 PRIOR to the first injection of CAM2038 and then at each visit thereafter (for women of childbearing potential).

^r It is the Investigator’s responsibility to understand and comply with all laws and regulations that apply to HIV, Hepatitis B, and Hepatitis C and testing of blood. Hepatitis B/C and HIV testing is required unless a site’s IRB prohibits such testing.

Study Phase:	Screening	Treatment Phase						EOT	Follow-up
Treatment:	-	CAM2038 q1w or q4w	CAM2038 q1w			CAM2038 q4w			All Subjects

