Study Population:	All Subjects ^a	All Subjects	New to BPN Treatment ^b	Transition from SL BPN/BPX ^c	Transition from CAM2038 q1w ^d	Transition from SL BPN/BPX (Monthly) ^e			
Month ^f :	M-1	M1	M1	M1 to Mx	M1 to Mx	Mx to M12 ^g	M1 to M12 ^h		M13
Week ^h :	-3	W1	W1	W2 to Wx ⁱ	W1 to Wx ⁱ	Wx to W48	W1 to W48	W49	W53
Day:	-	Day 1	Day 2-7 ^j	-	-	-	-		-
WPAI-GH	X	X		Monthly	Monthly	Monthly	Monthly	X	
Patient Satisfaction				Month 6	Month 6	Month 6	Month 6	X	
C-SSRS ^s	X	X		Weekly	Weekly	Monthly	Monthly	X	X
CAM2038 SC injection ^t		X	(X)	Weekly	Weekly	Monthly	Monthly		
Psychosocial Counseling		X		Monthly	Monthly	Monthly	Monthly		
Adverse Events ^u	X	X	(X)	Weekly	Weekly	Monthly	Monthly	X	X
Concomitant Meds/Procedures	X	X		Weekly	Weekly	Monthly	Monthly	X	X
On-site Visits	X	X	(X)	Weekly	Weekly	Monthly	Monthly	X	X

Abbreviations: BMI=Body Mass Index; COWS=Clinical Opiate Withdrawal Scale; C-SSRS=Columbia Suicide Severity Rating Scale; DSM-V=Diagnostic and Statistical Manual of Mental Disorders – Fifth Edition; ECG=electrocardiogram; HIV=Human Immunodeficiency Virus; Hx=history; ID= identification; M= month; SC=subcutaneous; SOWS=Subjective Opioid Withdrawal Scale; VAS=visual analogue scale; W= week; WPAI-GH=Work Productivity and Activity Impairment Questionnaire-General Health; (X)=optional visit based on individual subject titration needs.

^s Screening version at Visit 1 (Screening), Since Last Visit version at all subsequent visits.

^t CAM2038 q1w for weekly visits and CAM2038 q4w for monthly visits.

^u Any spontaneously reported adverse events will be recorded after the subject signs the informed consent form. In addition, adverse events will be elicited using a non-leading question each time the subject visits the clinic.

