9.3.4. Quality of Life Questionnaires and Patient Satisfaction Scale

Two quality of life questionnaires will be provided to subjects for completion:

- Work Productivity and Activity Impairment Questionnaire-General Health (WPAI-GH) (Reilly Associates).
- EQ-5D-5L Health Questionnaire (EuroQOL Group Association).

These are to be completed on a monthly basis, approximately every four weeks at the subjects scheduled visit.

A patient satisfaction scale will be provided to subjects for completion at month 6 and month 12 (EOT).

Copies of the WPAI-GH, EQ-5D-5L and patient satisfaction scale is provided in the Study MOP.

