9.4.4. Vital Signs

Vital signs will consist of temperature, blood pressure (systolic and diastolic blood pressure, mmHg), pulse rate (beats per minute), and respiratory rate (breaths/min) collected while sitting, following a rest period of at least 3 minutes.

9.4.5. 12-Lead Electrocardiogram (ECG)

12-Lead ECGs will be performed after the subject has been resting in a recumbent/supine position for at least 3 minutes. The ECG variables will include ventricular heart rate and the PR, QRS, QT, QTcB and QTcF intervals. The ECGs will be signed and dated by a medically-qualified individual to confirm review of the ECG and verify whether any abnormalities are clinically significant. In general, abnormal, clinically significant ECGs are expected to be associated with an item recorded in medical history or with an AE.

ECGs will be performed at Screening and at the EOT visit. In addition, ECGs will be performed after the first administration of CAM2038 q1w or CAM2038 q4w (i.e., prior to dosing at Week 2 for CAM2038 q1w or Week 5 for CAM2038 q4w). ECGs will also be performed in connection to dose increases (excluding the initial dose titration and booster injections) and after intake of QT-extending drugs or CYP3A4 inhibitors (a list of relevant drugs will be included in the Study MOP).

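### Withdrawal symptoms are barred from AE recording with no end date, yet no COWS/SOWS is marked after EOT, so in completers non-serious withdrawal starting later has no direct record

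*Protocol*

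**What the plan says.** **The bar.** Protocol 9.4.1.1 requires all AEs on the AE form except withdrawal symptoms, and gives the reason: "Withdrawal symptoms will be captured via specified assessments and should not be recorded as AEs". No time limit is attached.

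**The AE period.** The same section follows AEs from consent "until 14 days after the Follow-up Visit (or 30 days after early termination"). A footnote to Table 3 adds: "In addition, adverse events will be elicited using a non-leading question each time the subject visits the clinic". Table 3 marks AEs at Week 53.

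**The substitute.** The withdrawal scales are COWS and SOWS (9.3.5). Table 3 schedules them at Screening, Day 1, optionally on Days 2-7, monthly on treatment, and once more in a late column. Protocol 9.7 lists them as efficacy variables. The SAP reports them only in efficacy tables (14.2.6 and 14.2.7).

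**After treatment.** Section 7.1.3 moves subjects to standard care at Week 49. At Week 53, Table 3 marks only C-SSRS, AEs, concomitant medications and procedures, and the visit itself.

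**Early discontinuation.** Section 7.6 asks sites to keep collecting safety assessments, and adds: "The Investigator should also ask the subject to return for the Follow-up assessments, provided that the subject has not withdrawn consent for those assessments". It also mentions early termination procedures without listing them: "If a subject refuses to complete early termination procedures and/or Follow-up, this information will be recorded".

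**Tabulation.** SAP 11.1.2 puts in the summary tables only AEs with onset earlier than 30 days after the last dose.

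**The concern.** Leaving withdrawal out of the AE data is reasonable while a dedicated scale is measuring it. That justification ends when the scale stops, but the bar continues.

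Take a completer who tells the site at Week 53 of non-serious withdrawal that began after EOT. Followed as written, the protocol has the site ask the AE question, forbids entering the answer as an AE, and schedules no scale on which to score it. The event then appears in neither the AE tables nor the COWS/SOWS tables. The primary objective is safety and tolerability, and this interval follows the end of depot treatment, so the report would be silent on the point by construction.

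**Working it through.** The plan gives no figure on this point to reproduce. The check has two parts: which visit carries the last COWS/SOWS, and how many days follow it.

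**1. Which visit is last**

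- The Table 3 row for SOWS, COWS and VAS has a single late mark. In the text available for this review, the header of that page is misaligned, and the column carries both a Month 13 and a Week 49 label.
- The ECG and pregnancy-test rows have their late mark in the same column. Section 9.4.5 says "ECGs will be performed at Screening and at the EOT visit". The pregnancy footnote says "A serum pregnancy test will be performed at Screening and EOT (Week 49").
- On the Table 3 page where the Week 49 and Week 53 headers are intact, Patient Satisfaction has one late mark, under Week 49. Section 9.3.4 agrees: "A patient satisfaction scale will be provided to subjects for completion at month 6 and month 12 (EOT"). Rows that continue to Week 53 on that page carry two late marks.

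The last COWS/SOWS is therefore read as EOT, Week 49. This is a well-anchored inference, not a direct statement.

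**2. Length of the gap (completers)**

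Nominal day of Week k = 7(k − 1) + 1.

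| Event | Source | Day |
|---|---|---|
| Last q4w dose, Week 45 | Table 3 footnote | 309 |
| Last q1w dose, Week 48 | Table 3 | 330 |
| EOT, Week 49 | Table 3 | 337 |
| Follow-up, Week 53 | 7.1.3, Table 3 | 365 |
| End of AE collection | 365 + 14 | 379 |

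- AE collection after EOT: 379 − 337 = 42 days.
- Of these, up to Week 53: 365 − 337 = 28 days; then 14 more.
- COWS/SOWS scheduled in the 42 days: 0.

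**3. What the SAP cut-off would keep if these events became AEs**

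An AE is tabulated if onset falls before last dose + 30, so the last tabulated day is last dose + 29. If EOT falls g days after the last dose, onsets strictly after EOT keep 29 − g days, limited to 0-28 for the interval to Week 53.

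- q1w: g = 337 − 330 = 7, so 29 − 7 = 22 of 28 (days 338-359).
- q4w: g = 337 − 309 = 28, so 29 − 28 = 1 of 28 (day 338).

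Now apply the Table 3 windows to both the last dose and EOT, holding 28 days from EOT to Week 53:

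- q1w, ±3 days on each: g = 7 ± 6 = 1 to 13, keeping 28 down to 16 days.
- q4w, ±7 days on each: g = 28 ± 14 = 14 to 42, keeping 15 down to 0 days.

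**4. Early terminators, same cut-off**

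A subject who terminates g days after the last dose keeps 29 − g of the 30 days of AE collection: 29 if g = 0, 22 if g = 7, 1 if g = 28.

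Parts 3 and 4 measure what the fix would lose without a cut-off exemption. They do not measure the present gap.

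**The case against.** **The exclusion is deliberate and sensible.** Withdrawal belongs to the treated condition and has its own scales. EOT nominally falls a full dosing interval after the last dose, and later symptoms in completers arise under standard care, so they say less about CAM2038. This stands, and it keeps the point modest. It does not explain why the bar outlasts the scales.

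**Other records exist.** Serious withdrawal still goes on the AE form (9.4.1.2.1), and doubtful seriousness is to be reported. Concomitant medications and reasons for unscheduled contacts are recorded (9.3.7). This limits the gap to non-serious events. The remaining traces depend on someone acting and feed no withdrawal table.

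**General AE wording might override the bar.** Section 9.4 says that all AEs are recorded, and 9.4.1.1 includes findings the investigator thinks clinically significant. The specific exclusion is the more natural rule to follow; at best, sites would differ.

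**Section 7.1.2.3 lists COWS and SOWS at each visit.** That list concerns treatment visits, Weeks 2 to 48, so it does not reach Week 53.

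**Early terminators.** A reader might infer that they certainly have no withdrawal record and no planned handover, and that the gap is worst for them. The documents do not support this:

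- Section 7.6 continues safety assessments after study drug stops, and the 7.1.2.3 list names COWS and SOWS just before the remaining safety assessments. A site could reasonably carry the scales on.
- Early termination procedures are not itemised and may include a final scale.
- The synopsis, section 7.1 and SAP 4.3 intend return to usual care for all subjects; only the timing, Week 49, is tied to the end of treatment.

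**Conclusion.** The point holds for completers: under the rule as written, non-serious withdrawal starting after EOT has no direct record in the nominal 42 days of AE collection that remain. For early terminators the same gap is possible but not proven, because 7.6 does not say whether COWS/SOWS continue.

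The conclusion rests on reading the late COWS/SOWS mark as EOT, on nominal visit days, and on sites following the specific bar over the general AE wording.

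A reader might also infer a number of missed events, for instance from the planned 50% dropout. That would be unsupported: the documents give no rate of withdrawal after the depot, and dropouts include patients lost to follow-up. No rate or count is claimed. Severity is modest; the change is worth making because it is cheap and the primary objective is safety and tolerability.

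**What to change.** **Protocol 9.4.1.1**, add: *Withdrawal symptoms with onset after the EOT visit (or, for early terminators, after the last study visit at which COWS/SOWS is done) are recorded as AEs.*

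**SAP 11.1.2**, add a separate post-treatment row: number and percent of patients with such symptoms to the end of AE follow-up, by last product received. State that the row is exempt from the 30-day cut-off.

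**Cost.** One sentence and one table row, with no new visit or instrument, since the AE question is already asked at Week 53. There would be a few more mild records, some under standard-care buprenorphine with weak attribution to CAM2038, and a definition that differs from the on-treatment one. On-treatment AE rates are unchanged because the row is separate.

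**Limits.** Patients who cannot be reached still give no data, and no contact is scheduled in the last 14 days.

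**Alternative.** Adding COWS/SOWS at Week 53 keeps one definition but adds a procedure. COWS rests on a timed observation at the visit, whereas an AE record gives onset and resolution dates.
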